5. METHODS

5.1 Study parameters/endpoints

5.1.1 Primary outcome parameters

○ Severity of PTSD (DSM-5) as measured with:

- CAPS-5 (Clinician Administered PTSD Scale, Weathers et al., 2014, Boeschoten et al., 2014). The first psychometric evaluation of the CAPS-5 showed good reliability, convergent and divergent validity (Weathers et al., 2017). Severity of PTSD is measured on a continuous scale on the CAPS-5. All 20 symptoms of PTSD from the DSM-5 are assigned a severity score of 0-4. These 20 scores are then summed to calculate total PTSD symptom severity.

5.1.2 Secondary outcome parameters

○ Presence of PTSD (DSM-5) as measured with: CAPS-5 (Clinician Administered PTSD Scale, Weathers et

al., 2014, Boeschoten et al., 2014)

○ PCL-5 (PTSD Checklist for DSM-5; Weathers et al., 2013; Boeschoten et al., 2014; Bovin et al., 2016).

- Presence and severity of personality disorders as measured with the SCID-5-PD (Structured Interview for DSM-5 Personality Disorders; First et al 2016) to assess presence and severity (dimensional score) of the DSM-5 personality disorders
- Demographic questionnaire

- Outcome Questionnaire -45 (OQ-45), with 25 items on psychiatric symptoms and 20 on interpersonal, occupational and social functioning (de Jong et al., 2008)
- BDI (Beck Depression Inventory, Beck et al., 1988)
- AUDIT (Alcohol Use Disorders Identification Test, Babor et al., 2001) to assess alcohol and drug abuse
- SCID-5-S (American Psychiatric Association, 2017).
- WHODAS 2.0 (World Health Organization Disability Assessment Schedule, Ustun et al 2010)
- EQ-5D-5L (<http://www.euroqol.org/eq-5d-products/eq-5d-5l.html>) to measure quality-adjusted life year (QALY)
- Tic-P (Trimbos/iMTA questionnaire for costs associated with psychiatric illness) for health care consumption (Hakkaart-van Roijen et al., 2002)
- NSSI screening; Screeningsvragenlijst opzettelijk zelfverwondend gedrag (Baetens & Claes, 2014) to assess selfinjury.
- SMI-118 (Schema Mode Inventory 118 items, Young, Arntz, Atkinson, Lobbestael, Weishaar, Van Vreeswijk & Klokman, 2008).
- YSQ-75 (Young Schema Questionnaire 75 items, Young & Brown, 1998).
- The ITQ (International Trauma Questionnaire) assesses PTSD and complex PTSD (CPTSD) symptoms according to the diagnostic formulation published in the ICD-11 (Karatzias et al., 2016; Cloitre et al., 2018). Since the CAPS-5 will be used to assess PTSD in the current study, patients will be asked to only complete the CPTSD items of the ITQ. The ITQ measures CPTSD through six five-point Likert scale (0-4) items related to three symptom clusters of difficulties in emotion-regulation (C1-2), negative self-concept (C3-4) and disturbed relationships (C5-6). Additionally, three five-point Likert scale items assess functional impairment (social, occupational and other important areas of life) associated with CPTSD symptoms (C7-9). A diagnosis of CPTSD requires that criteria for a PTSD are met (as measured by the CAPS-5), as well as a

score of ≥ 2 in each of the three CPTSD symptoms clusters, plus functional impairment associated with these symptoms. A patient can only receive a PTSD or a CPTSD diagnosis, not both. The ITQ has demonstrated adequate internal reliability and validity (Cloitre et al., 2018; Hyland et al., 2017).

5.1.3 Biological predictors (see table 2):

- Biological parameters
 - Body measures: Weight, height, blood pressure
 - HPA axis (cortisol): Hair sample
 - Biomarkers: Fasting blood sample (BDNF, FKBP-5) & Full blood
- MRI session in subsample (60 min)
 - 3 Tesla-MRI (GE, VUmc): functional MRI with a face recognition , Structural MRI, Resting state MRI, DTI. In between scans a visual analogue scale (VAS) will be applied to assess distress during the scan session.

5.1.4 Psychological predictors ○ Trauma

exposure as measured with:

- CTQ (Child Trauma Questionnaire, Bernstein et al., 2003), 28-item questionnaire to check self-reported child trauma experiences, with 5 subscales: physical, emotional and sexual abuse, physical and emotional neglect (5-point Likert scale), and 3-item scale to detect under-reporting
- LEC-5 (Life Events Questionnaire, Weathers et al., 2013).
- Cognitive factors
 - DERS (Difficulties in Emotion Regulation Scale; Gratz & Roemer, 2004; Lavender et al., 2015) a 36-item self-report measure that assesses state levels of emotion dysregulation across six domains: non-acceptance of negative emotions, difficulties engaging in goal-

directed behaviors when distressed, difficulties controlling impulsive behaviors when distressed, limited access to effective emotion regulation strategies, lack of emotional awareness, lack of emotional clarity (5-point Likert scale).

-
- PAI-BOR (Personality Assessment Inventory- Borderline features scale, Distel, de Moor & Boomsma, 2009) to measure severity of borderline personality disorder symptoms. The PAI-BOR consists of 24 items rated on a 4-points Likert scale. It measures four domains of BPS, affective instability, identity problems, negative relations and self harm.
- Stop/signal task as a measure for interference/working memory.
- Affective factors (Hyper-arousal: anger, sleep; hypo-arousal: dissociation)
 - STAS (State-Trait Anger Scale, Spielberger et al., 1994) on trait and state anger with 10 items per scale using a 4-points scale.
 - PSQI (Pittsburg Sleep Quality Index, Buysse et al., 1989) with 4 items on sleep time and 6 associated items (4-points scale).
 - DES-II (Dissociative Experiences Scale; Bernstein & Putnam 1986), 28items to asses dissociative symptoms.
- Relational factors (therapeutic alliance, attachment, social support) as measured with:
 - WAI (Working Alliance Inventory, Horvath & Greenberg, 1992; in Dutch: Werk Alliantie Vragenlijst, WAV, Vertommen & Vervaeke, 1990), 12-items
 - RSQ (Relationship Scale Questionnaire, Griffin & Bartholomew, 1994) contains 30 statements on attachment rated on a 5-point scale
 - CPI (Close Person Inventory, Stansfeld & Marmot 1992) to assess social support.
 - Therapists will be asked to rate to which extent they believe in the effectiveness of the protocol, on a scale of 1 to 10.

Table 1: Overview of measurements: interviews and questionnaires

MEASUREMENTS				To	T1	T2	T3	T4	FU
TIME POINTS (months)				0	3	6&	9	12	18
SCREENING	ROM Questionnaires	Items							
Psychiatric symptoms	OQ-45.2 (1996)	45	SR	X*	X	X	X	X	X
PTSD symptoms	PCL-5 1.1 (2014)	22	SR	X*	X	X	X	X	X
PD symptoms	SCID-5-PD screener	119	SR	X					
Axis I disorders	SCID-5-S screener	??		X*					
INTERVIEWS	DAY 1	Semi-structured interviews	Duration	Type					
PTSD	CAPS-5 1.2 (2015)	45 min	INT	X		X		X	
Axis I-disorders	SCID-5-S	45 min	INT	X*#				X	
Personality disorders	SCID-5-PD	120 min	INT	X#				X	
QUESTIONAIRES	DAY1	Additional questionnaires	Items						
Demographics	Demographic questionnaire PROSPER (2017)	30	INT	X*					
Life events	LEC-5 1.1 (2014)	17	SR	X*					
Child trauma	CTQ (NESDA 2004)	25	SR	X					
Emotion regulation	DERS NL (2004)	36	SR	X		X		X	
Complex PTSD	ITQ (2018)	9	SR	X		X		X	
Anger	STAS NL (ZAV 1982)	10	SR	X		X		X	
Sleep	PSQI NL (1989)	10	SR	X		X		X	
Dissociation	DES-II (1986)	28	SR	X		X		X	
Depression severity	BDI-II (2002)	21	SR	X		X		X	
Alcohol / drugs	AUDIT (MATE-nl 2.1 2010)	10	SR	X		X		X	
Self harm behaviour	NSSI screening (NL versie 2014)	7	SR	X	X	X	✘	X	X
Borderline personality symptoms	PAI-BOR (2009)	24	SR	X		X			✘

DAY2	Additional Questionnaires								
Therapeutic alliance	WAV (1990)	12	SR		✗	X	X		
Attachment	RSQ (1994)	30	SR	X		X		X	
Social support	CPI (NESDA 2004)	4	SR	X		X		X	
General functioning	WHODAS 2.0 (2014)	12	SR	X		X		X	X
Quality of life	EQ-5D-5L 2 (2010)	9	SR	X		X		X	X
Health care consumption	Tic-P (2012)	32	SR	X		X		X	X

AUDIT = Alcohol Use Disorders Identification Test; BDI = Beck Depression Inventory;; CPI = Close Person Inventory; CTQ = Child Trauma Questionnaire; DES-II = Dissociative Experiences Scale; INT = interview; LEC-5 = Life Events Checklist; SCID-5-S; OQ-45 = Outcome Questionnaire 45; PCL-5 = PTSD Checklist for DSM-5; PSQI = Pittsburg Sleep Quality Index; ROM = Routine Outcome Measurement; RSQ = Relationship Scale Questionnaire; DERS = Difficulties in Emotion Regulation Scale; ITQ = International Trauma Questionnaire; SR = self-report questionnaire; SCID-5-PD = Structured Clinical Interview for DSM-5 Personality disorders; STAS = State Trait Anger Scale; Tic-P = Trimbos/iMTA questionnaire for costs associated with psychiatric illness; WAI = Working Alliance Inventory, WHODAS = World Health Organization Disability Assessment Schedule 2.0.; NSSI = Non Suicidal Self-Injury screener; PAI-BOR: Personality Assessment Inventory- Borderline features scale.

* Healthy controls will only fill out these questionnaires and interviews

⊗ Timing of the T2 measurement will be directly after trauma treatment, around 6 months

#The SCID-5-P at T0 is part of the regular intake procedure at the Sinai Centre

Table 2: Overview of add-on cognitive task, biological measurements, including MRI

MEASUREMENTS		DURATION	To	T1	T2	T3	T4	FU
in months			0	3	6 [⊗]	9*	12	18
COGNITIVE TASKS AT DAY 2		10 min						
Working memory	N-back	10	X*					
Interference	Stop/Signal task	15	X*					
PHYSICAL EXAMINATION AT DAY 2		30 min						
Body measures	Weight, height	10	X					
Blood pressure	Systolic and diastolic	5	X					
HPA axis (Hair)	Hair sample (cortisol)	5	X		X			
Biomarkers	Fasting blood sample (5HTTLPR, BDNF, FKBP5, oxytocin/OXTR) & Full blood	10	X		X			
MRI SESSION IN SUBSAMPLE WITHIN 2 WEEKS		60 min						

Functional MRI	Face recognition task	15	X		X			
Structural MRI		7	X		X			
Resting state MRI		10	X		X			
DTI		10	X		X			

DTI = Diffusion Tensor Imaging, MRI = Magnetic Resonance Imaging.

[&] Timing of the T2 measurement will be directly after trauma treatment, around 6 months

* Timing of the T3 measurement will be 3 months after T2, around 9 months

Table 3: Overview of duration of measurements (in minutes)

	To	T1	T2	T3	T4	Follow-up
Interviews	45	-	45	-	195	-
Questionnaires	91	15	88	15	88	27
n-back	10	-	-	-	-	-
TOTAL	141 (ca. 2.5 hrs)	15	128 (ca. 2 hrs)	15	278 (ca. 4,5 hrs)	27
Blood/hair	30	-	30	-	-	-
MRI	90	-	90	-	-	-
TOTAL for subgroup with MRI/blood/hair	261 (ca. 4 hrs)	15	218 (ca. 3,5 hrs)	15	278 (ca. 4,5 hrs)	27

5.2 Randomisation, blinding and treatment allocation

5.2.1 Randomization

An independent central research assistant will randomize participants to condition after checking all in- and exclusion criteria. Randomization will be based on block randomization (n=4 per block) per site, to guarantee a balance between conditions per site and over time. For both RCTs there will be a separate randomization procedure depending on comorbid PD diagnosis:

- A1. If PTSD + BPD: EMDR vs. integrated DBT-EMDR
- A2. If PTSD + CPD: ImRs vs. integrated SFT-ImRs.

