treatment (1.0), the number of persons needed to include is 50 persons per condition to reach for 80% power. Expecting a dropout rate of 25%, we will include 63 persons per arm, for 4 arms a total of 252 adult patients with PTSD and - at least 4 - PD symptoms. Of these patients, 80 next to 40 healthy matched controls will be asked for additional MRI research before and after treatment. In total, 292 persons will be included in this study.

Intervention: In patients with PTSD and BPD: EMDR (3-6 months plus 6-9 months treatment pause) compared to integrated DBT-EMDR (12 months); in patients with PTSD and CPD: ImRs (3-6 months plus 6-9 months treatment pause) compared to integrated ImRs-SFT (12 months).

Main study parameters/endpoints: Primary outcome measure is PTSD symptom severity after 12 months. Secondary outcome measures are PD symptoms (SCID-5-PD), disability (WHODAS), quality of life (EQ-5D-5L) and health costs (Tic-P). At baseline (T₀) and after 12 months (T₄) clinical interviews (CAPS-5, SCID-5-PD dimensional score) and self-rating scales (PCL-5) will be used. After 3 (T₁), 6 (T₂), 9 (T₃), and 18 months (follow-up), questionnaires only will be used. At baseline, candidate predictors will be measured including above mentioned cognitive, affective, relational factors, and hormonal and epigenetic factors. In a subgroup, structural and functional MRI, with resting-state and an emotion processing (face recognition) will be performed.

Nature and extent of the burden and risks associated with participation and benefits:

The burden and risks associated with participation in this study is reasonable. All patients will receive psychotherapy, which is considered to be the most effective treatment for PTSD and PD. There is evidence that all four conditions are therapeutic in patients with PTSD and PD and no evidence yet what condition is more effective. Total time of the six measurements is approximately 5 hours per patient for interviews and 5 hours for questionnaires (see table 3), which are partly part of the routine outcome measurements (ROM). Questionnaires can be filled in at home. On the one hand, extensive clinical interviews and self-rating scales can be felt as disturbing because of fatigue, taken time and emotional burden. On the other hand, patients may feel well recognized by the time taken by specialized clinicians for them. Assessors will be well-trained and work in close

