4.3 Exclusion criteria

A patient who meets any of following criteria will be excluded from participation in this study:

- Current psychosis
- Comorbidity interfering with treatment or randomisation (severe outward aggression, antisocial PD, treatment interfering addiction or eating disorders, somatic problems)
- Primary diagnosis of paranoid, schizoid, schizotypal, narcissistic, histrionic or antisocial PD
- Mental retardation

For the healthy controls, current psychiatric diagnosis is an exclusion criterion.

For the subgroup of patients and controls that also undergo MRI examination more exclusion criteria are: Pregnancy; Metal implants (such as pacemakers, etc.); Somatic disorders interfering with brain functioning; Claustrophobia; Other psychopharmaca than at-least-3months stabile dose SSRI or low-dose benzodiazepines

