4.4 Sample size calculation

A power calculation was made based on Twisk (2007). We assume that PTSD treatment (EMDR or ImRs) have a small effect size (< 0.5) in the complex patient group with PTSD and comorbid

CPD/BPD, while the integrated treatment will show double effect sizes (1.0) (Harned et al., 2014). With a minimal clinical relevant difference of a 0.5SD on the CAPS-5, and the assumptions of a SD of 20.0, an intra-person correlation coefficient of 0.7, 5 follow-up measurements, the needed number to include is 50 persons per condition to reach for 80% power. Expecting a drop-out rate of 25%, we will include 63 persons per arm, or for 4 arms in total 252 persons.

In 2016, approximately 950 new patients were referred to the SC (Amstelveen). From these patients, ca. 450 had PTSD. From these PTSD patients, 168 had a comorbid PD and 188 more were not assessed for personality traits (“Uitgestelde diagnose”). We expect that introducing the assessment of axis II assessments with this study will result in an estimated 300 patients with PTSD and PD per year, and after 33% refusals or exclusions, in an estimated 200 patients possible to include per year. To be sure to include enough patients, we will need to include more patients from another site of the

Sinai Center, i.e. Amersfoort (400 patients, from which 216 PTSD patients, from which an estimated 100 PTSD + PD patients), and extend the inclusion period.

From these 252 patients, 80 will be asked for additional MRI, next to 40 healthy controls (Total sample size = 292). An estimated 40 patients will be available for a second MRI after 6 months (total of 160 scan sessions).

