5.2.2 Unblinding Procedure

Blinding of participants and therapists to condition is not possible as it will be clear to both therapists and patients which treatment is given.

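### A fixed, stated block size of 4 per site and RCT in an open-label trial makes up to a third of allocations inferable by anyone who tracks a list; varying, undisclosed sizes would largely remove that certainty

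*Combined protocol and SAP*

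**What the plan says.** Section 5.2.1 sets the method in one sentence: "Randomization will be based on block randomization (n=4 per block) per site". The stated purpose is "to guarantee a balance between conditions per site and over time". It adds: "For both RCTs there will be a separate randomization procedure depending on comorbid PD diagnosis". There is therefore one list for each combination of site and RCT. Section 4.4 says of recruitment that "we will need to include more patients from another site of the" centre. That makes two sites and, with two RCTs, four lists.

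An independent central research assistant randomises once all eligibility criteria have been checked (section 5.2.1). Section 5.2.2 says that "Blinding of participants and therapists to condition is not possible".

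Section 5.3 describes how patients enter. An intake psychologist hands out the information, a researcher explains the study, and at least a week passes. At T0, consent is taken and eligibility is checked again. The T0 CAPS-5 follows inclusion, but the text does not say whether it comes before or after allocation.

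Nothing in the text varies the block size or withholds it from staff. Section 9.2 has investigators trained in all study procedures, with no exception for this one.

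**The concern.** Concealing a list and making it unpredictable are separate protections. A central assistant gives the first. The second depends on whether the next place can be deduced from places already filled. When every block is known to hold two of each arm, the last place is always forced and the third sometimes is. Here earlier allocations become known through the treatment given: one arm is a course of at most six months, the other a year of at least two sessions a week.

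At stake is the comparability of the arms. If someone who influences entry expects a particular arm, a patient may be brought forward, held back or judged ineligible because of it. Section 4.3 leaves some room for this with the exclusion "Comorbidity interfering with treatment or randomisation". A bracketed list of conditions follows and narrows the criterion, but how severe or disruptive a condition must be remains a judgement.

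The model in section 7.1 adjusts for baseline score, severity, sex and age. Selection on traits outside the model, such as motivation or expected adherence, would stay in the treatment contrast.

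**Working it through.** The plan gives no predictability figure, so there is none to reproduce.

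**Inputs**
- Block size: 4, fixed (section 5.2.1).
- Allocation ratio: 1:1, so two places per arm in each block. This is inferred from "we will include 63 persons per arm, or for 4 arms in total 252 persons" (section 4.4) and the balance aim; the ratio itself is not written out.
- Total: 252, or 126 per RCT.

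**Certain allocations with complete tracking.** A balanced block of 4 has 6 equally likely orders. AABB and BBAA each leave 2 forced places; the other four orders each leave 1.

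- Mean forced places per block: (2×2 + 4×1)/6 = 4/3.
- Share: (4/3)/4 = 1/3, or 33.3%.
- Number: 126/3 = 42 per RCT and 252/3 = 84 overall, if all blocks are complete.

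With four lists of 63 (an assumed even split), each has 15 full blocks and 3 further places. The number is then 4 × (15 × 4/3 + 1/3) = 81.3, so 84 is the upper figure.

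**Best guess.** The observer picks the arm with more places left and tosses a coin when they are equal.

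| Place in block | All earlier places seen | One unseen | Two unseen |
|---|---|---|---|
| 1 | 1/2 | 1/2 | 1/2 |
| 2 | 2/3 | 1/2 | 1/2 |
| 3 | 1/3×1 + 2/3×1/2 = 2/3 | 2/3 | 1/2 |
| 4 | 1 | 1/3×1 + 2/3×1/2 = 2/3 | 2/3 |
| Mean correct | 17/24 = 70.8% | 58.3% | 54.2% |
| Certain | 33.3% | (1/3)/4 = 8.3% | 0% |

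The columns for unseen allocations apply when the observer must decide before learning the one or two allocations just ahead of the patient in question.

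**Other designs.** Exact enumeration for larger fixed blocks gives 25% certain and 68.3% correct for size 6, and 20% and 66.6% for size 8. For randomly varying sizes, 3,000 lists of 63 were simulated. The observer knew the full history and the set of possible sizes, but not the current size.

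| Sizes | Certain | Best guess correct |
|---|---|---|
| Fixed 4 (same simulation) | 32.3% | 70.4% |
| 4 and 6 at random | 5.6% | 68.9% |
| 4, 6 and 8 at random | 2.3% | 67.7% |

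The simulated fixed-4 figure lies just below one third because the last block of 63 is incomplete. Varying the size removes most of the certainty; the accuracy of an informed guess changes little.

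**The case against.** The strongest reply is that one third is a ceiling few people could reach. It needs someone who knows the block size and every earlier allocation, in order, in one of two interleaved lists at the site. The text does not say that anyone keeps such a record. This stands, and the figures should be read as maxima.

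The second reply concerns timing. Section 4.4 projects 200 includable patients a year at the first site. With an even split between the RCTs (an assumption), that is 100 per list per year, or 100/52 = 1.9 a week. With at least a week between information and decision, about two allocations could fall in between, and at two unseen nothing is certain. This largely answers the risk at first approach. It does not cover the later steps, when a consenting patient is scheduled and eligibility is checked again, and slower accrual would weaken it.

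Third, the independent assistant already allocates after the eligibility check. That is a real safeguard, but it controls the list and not what open treatment reveals about it.

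A reader might also infer from the Summary's remark that "Assessors will be well-trained and work in close" connection with the treatment teams that allocations are visible to those deciding entry. The remark belongs to a discussion of patient burden and does not say that assessors know arms or allocation order. Section 6.2.2 has therapists meet researchers weekly, and section 5.3 has researchers explain the study to candidates. That shows a possible route for the information, not that it is used.

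**Conclusion.** The point holds as an avoidable risk, not as evidence of bias. A fixed, stated block of 4 in an open-label trial makes up to one third of allocations certain (at most about 84 of 252) and about 71% guessable for a complete tracker of a site-by-RCT list. One unseen allocation reduces these to about 8% and 58%, two to 0% and 54%. The arithmetic is exact given 1:1 blocks. How far staff could track the lists is not known from the documents. Covariate adjustment would remove part of any resulting bias.

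Three stronger readings are not supported:
- That staff can in practice predict a third of allocations. This takes the ceiling for the expected value.
- That the block size was public during recruitment. The text shows only that it is in the protocol and that investigators are trained in the procedures.
- That patients with both borderline and cluster C features can be steered to either RCT because no rule places them. Section 5.2.1 allocates by comorbid diagnosis, and the flow chart in Figure 2 is missing from the text reviewed, so the absence of a rule cannot be confirmed. Varying the blocks would not cure such a gap in any case.

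The change is worth making because it is cheap; the plan is not invalid without it.

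**What to change.** In section 5.2.1, replace the fixed block of 4 with randomly varying block sizes (for example 4, 6 and 8) within each site-by-RCT list, generated by someone outside recruitment. Say in the protocol only that sizes vary, and hold the sizes in a document that recruiting and treating staff do not see. Keep allocation by the independent assistant after the eligibility check, and add that the T0 CAPS-5, the model's baseline score, must be recorded before the allocation is issued.

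The cost is a new list for allocations still to be made, a short text change and a fixed order of steps at T0. The largest possible end imbalance rises from 2 to 4 per list; with two sites, from 4 to 8 per RCT of 126 in the worst case. A larger fixed block is a weaker alternative: size 8 still leaves 20% of allocations certain.
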